### 8.5. Replacement of individual subjects after withdrawal

Patients that meet the inclusion criteria will be invited for participation in the study. When a patient agrees to participate in the study, patients will be invited for screening and informed consent is signed. After the screening visit, eligible patients will proceed to the second visit. When patients decide to withdraw after start of the treatment period, they will be replaced so that twenty patients will complete the full study protocol.

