#### 3.1. General Design and Plan

Subjects with UACR >20 mg/g (2.26 mg/mmol) with a diagnosis of type 2 diabetes who meet the inclusion criteria will be invited for screening. After the screening visit, eligible patients will proceed to the randomization visit. Patients will be randomly assigned to a cross-over study consisting of two periods of 1-week treatment with dapagliflozin and two periods of 1-week treatment with placebo in random order with a 1-week wash-out period between every treatment period to avoid cross-over effects. Based on a prior study, effects of dapagliflozin on UACR, blood pressure, body weight, fasting plasma glucose and eGFR were fully present after 4 days. We will therefore ask patients to collect urine after 3, 5, 6, and 7 days. Due to day-to-day variation in UACR we are collecting multiple urine samples to increase precision and therefore collect urine at 3, 5, 6, and 7 days. We will also collect urine after 1 day to further delineate the time-course of the response to dapagliflozin and assess if the treatment effect on UACR is directly present after 1 day. Blood pressure and body weight will be recorded, and blood samples will be taken at the time points described below and in the table. Overall, a 1-week treatment period is considered sufficient to detect effects on primary and secondary outcomes.

Since data collection will be performed at home using wearable devices and digital technologies, instructions will be provided during the randomization visit to perform data collection and study procedures at home. Data collection and measurements will be performed in each treatment period as indicated in Figure 1. Bottles with smart caps that

Statistical Analysis Plan Page 4 of 13

allow real-time monitoring of adherence, blood pressure monitors, body analysis scales and study medication will be provided at the randomization visit. Patients receive four numbered bottles with seven tablets in each bottle, according to their randomized treatment schema. Patients will be instructed to take the study medication once daily, in the morning.

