#### 3.2. Sample Size

The sample size for this study is based on the hypothesis that the response to dapagliflozin is reproducible upon re-exposure and thus correlates between the first and second exposure while no correlation will be detected during placebo patients. A prior retrospective study found that during intervention in the renin-angiotensin-system responses in proteinuria correlate with correlation coefficients ranging between 0.7 to 0.9. Since this was a retrospective study, we assume a more conservative correlation coefficient of 0.6. A sample size of 20 patients provides >80% power (alpha 0.05) to detect a correlation coefficient of 0.6.

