#### 5.1. Analysis of primary and secondary study outcome

The change from baseline in UACR will be calculated using the values collected at day 5, 6 and 7 of each treatment and wash-out period. Because of the skewed distribution UACR will be log-transformed before analysis. The geometric mean of these 3 values (at baseline to end of treatment) will be calculated as log(UACRend/UACRbaseline) and the geometric mean change from baseline will be determined.

The study has two cycles of two treatment periods (dapagliflozin and placebo). For the calculation of response, the difference in log-transformed UACR change between dapagliflozin and placebo will be calculated during the first and second cycle. Patient level Bayesian analysis:

First, a Bayesian analysis will be conducted to calculate the posterior probability of dapagliflozin producing a clinically meaningful response on UACR within each individual patient relative to placebo for both treatment cycles combined. Thus for every patient, data of each cycle is combined and expressed in the form of a likelihood function with non-informative priors to calculate the posterior distribution. A clinically meaningful response on UACR is defined as the placebo subtracted percentage UACR change during the first and second cycle with different thresholds of 10%, 20% or 30% reduction in UACR. Population level Bayesian hierarchical analysis:

Subsequently, individual patient results on UACR will be combined to conduct a Bayesian hierarchical analysis to calculate the posterior probabilities of a clinically meaningful response at the population level (10%, 20%, and 30%). Therefore, responses on UACR from each patient will be aggregated into a sample mean and variance, assuming a normal distribution centred around the patient's true mean effect and variance. The Bayesian hierarchical model is defined as:

$$Y_{ij} \sim N(\alpha_i + \beta_i X_{ij}, \sigma_i).$$

Were  $Y_{ij}$  is the placebo subtracted UACR response for the  $i^{th}$  subject at time j and is described by  $x_{ij}$  ( $x_{ij}=1$  if treated with dapagliflozin; =0 if placebo treated). The subject specific intercept and slope were modelled as  $a_i \sim N(a_0, \tau_a^2)$  and  $\beta_i \sim N(\beta_0, \tau_\beta^2)$  respectively. Again, we used non-informative prior for  $a_0$ ,  $\beta_0$ ,  $\tau_a^2$ ,  $\tau_\beta^2$ ,  $\sigma_i$ .

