#### Heterogeneity treatment of effect analysis:

For those patients that completed both treatment cycles we will evaluate heterogeneity of treatment effects (HTE) across patients using a linear regression model with UACR response as the outcome. The model includes fixed effects for treatment and subject and a treatment-by-subject interaction, this allows each participant to have a different treatment effect. The statistical significance of patient-level HTE will be assessed by a likelihood test for the interaction term. In addition, we also fit a generalised linear mixed effect (LME) model with a random intercept and slope (for the treatment effect) to estimate the average treatment effect across all subjects. Fixed effects include treatment sequence, and treatment cycle in combination with an unstructured covariance structure.

Also we will use the linear mixed effects model as described above to determine if there is within individual variation in treatment response, we will fit a linear mixed model with correlated random intercepts and random slopes for treatment and include treatment period as a fixed effect. Subsequently, we will compare (using a maximum-likelihood ratio fit test) this model against a random intercept only model with treatment and treatment period as fixed effects.

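### The likelihood-ratio test for a random treatment slope has no stated reference distribution, and the customary chi-square on 2 degrees of freedom would be conservative: a true size of about 2.5% to 3.4% against a nominal 5%

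*Combined protocol and SAP*

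**What the plan says.** Under the heterogeneity heading of SAP 5.1, the larger model is set out as follows: "we will fit a linear mixed model with correlated random intercepts and random slopes for treatment and include treatment period as a fixed effect". The plan will then "compare (using a maximum-likelihood ratio fit test) this model against a random intercept only model". Protocol 10.1 describes the same comparison under the primary parameter. Neither section gives a reference distribution, degrees of freedom, a critical value or an alpha for this test. As written, the larger model lists only period as a fixed effect, while the smaller lists treatment and period.

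The same part of the SAP also plans a regression with fixed treatment, subject and treatment-by-subject terms: "The statistical significance of patient-level HTE will be assessed by a likelihood test for the interaction term".

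Each patient receives "two periods of 1-week treatment with dapagliflozin and two periods of 1-week treatment with placebo in random order", which SAP 5.1 groups into two cycles holding one period of each treatment. On size, SAP 3.2 and protocol 4.4 state: "A sample size of 20 patients provides >80% power (alpha 0.05) to detect a correlation coefficient of 0.6". Under protocol 8.5, patients who withdraw after treatment starts are to be replaced: "they will be replaced so that twenty patients will complete the full study protocol".

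**The concern.** The random slope adds two parameters: its variance and its covariance with the intercept. If patients do not differ in response, the slope variance is zero. A variance cannot be negative, so the null value lies on the boundary of the parameter space and the usual chi-square theory for likelihood ratios fails. The statistic then behaves approximately as an equal mixture of chi-square(1) and chi-square(2). An analyst who counts two extra parameters and reads the statistic against chi-square(2) gets p-values that are too large.

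The protocol's rationale for this design is that parallel-group trials cannot separate true variation in drug response from random variation. This test addresses that question directly. The number of completers is fixed at 20, so power lost through the reference distribution cannot be recovered by recruiting more patients. Because the reference is unstated, it could also be chosen after the statistic has been seen.

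**Working it through.** **Inputs from the documents.** There are 20 completing patients (protocol 8.5, SAP 3.2). Each has four treatment periods, two on dapagliflozin and two on placebo (SAP 3.1), so there are 20 × 4 = 80 period-level responses. Alpha is 0.05 and the planning correlation is 0.6 (SAP 3.2).

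**Assumptions.** Each cycle holds one period of each treatment. Both models hold treatment and period as fixed effects and are fitted by maximum likelihood. The 5% level is borrowed from the sample-size section. The documents give no variance components, so several ratios were tried.

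**1. The plan's own figure.** Using Fisher's z, power = Φ(√(N−3) × atanh(r) − z). With N = 20 and r = 0.6 this is Φ(4.123 × 0.693 − 1.960) = Φ(0.898) = 81.5% two-sided, or 88.7% one-sided. The N required for 80% two-sided is 19.3. The stated figure reproduces, but it concerns the cycle-to-cycle correlation. No power or size is stated for the likelihood-ratio test.

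**2. Asymptotic size.** Size at cut-off c = 0.5 × P(χ²₁ > c) + 0.5 × P(χ²₂ > c).
- Chi-square(2), c = 5.991: 0.5 × 0.0144 + 0.5 × 0.05 = 3.2%.
- Mixture, c = 5.138: 5.0% by construction.
- Chi-square(1), c = 3.841: 0.5 × 0.05 + 0.5 × 0.1465 = 9.8%.

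**3. Size with 20 patients.** 10,000 null trials per row; simulation standard error about 0.2 points.

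| Intercept SD ÷ residual SD | chi-square(2) | mixture | chi-square(1) |
|---|---|---|---|
| 0 | 2.5% | 3.6% | 7.1% |
| 0.3 | 2.5% | 3.8% | 7.0% |
| 1 | 3.2% | 4.8% | 9.0% |
| 2 | 3.4% | 5.0% | 9.6% |
| 1, with cycle in place of period | 3.1% | 4.5% | 8.7% |

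**4. Power.** Within a cycle, the dapagliflozin-minus-placebo difference has variance τ² + 2σ², where τ is the slope SD and σ the residual SD. The two cycle responses therefore correlate at r = τ²/(τ² + 2σ²). Setting r = 0.6 gives τ² = 3σ², so τ = 1.73σ. The rows below use intercept SD = σ and 10,000 trials each, with a standard error of 0.5 points or less.

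| τ ÷ σ | r | chi-square(2) | mixture | gain |
|---|---|---|---|---|
| 0.7 | 0.49/2.49 = 0.20 | 18.6% | 24.0% | 5.4 |
| 1.0 | 1/3 = 0.33 | 46.5% | 53.1% | 6.6 |
| 1.73 | 0.60 | 95.0% | 96.2% | 1.2 |

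**5. A cross-check on the log-albuminuria scale.** Protocol 6.3 reports a 36.2% fall in 24-hour albumin excretion (95% CI 22.9 to 47.2) in 33 completers. The log interval runs from ln(0.528) = −0.639 to ln(0.771) = −0.260, so the standard error is 0.379/3.92 = 0.0966. If the analysis was paired, the SD is 0.0966 × √33 = 0.555. An assumed cycle-to-cycle correlation of 0.43 gives τ = √(0.43 × 0.308) = 0.364 and σ of about 0.30. In 1,500 trials per row:

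| Slope SD (log units) | r | chi-square(2) | mixture | gain |
|---|---|---|---|---|
| 0.15 | 0.11 | 11% | 15% | 4 |
| 0.25 | 0.26 | 48% | 55% | 7 |
| 0.36 | 0.42 | 86% | 90% | 4 |

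With an intercept SD of 0.15, the middle row becomes 40% against 47%. Null trials on this scale (4,000 per setting) gave sizes of 2.8% to 3.0% for chi-square(2) and 4.0% to 4.9% for the mixture, in line with step 3.

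**The case against.** A reader might infer that the plan prescribes an ordinary chi-square(2) test, and so has one known true error rate below 3%. The documents do not support this. They name no reference at all, and the size under chi-square(2) moves with an intercept variance that they do not give. Even the direction of the error is open. Taken literally, the larger model gains two covariance parameters but does not list the fixed treatment effect, so a mechanical count gives a difference of one. A chi-square(1) reference would be anti-conservative, at 9.8% asymptotically. The figures for chi-square(2) apply once the two models share their fixed effects.

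A reader might also infer that this test decides whether patients truly differ. It does not. SAP 5.1 puts the Bayesian patient-level and hierarchical analyses first. It adds the cycle-to-cycle correlation, on which the sample size rests, and assigns the significance of patient-level heterogeneity to the fixed interaction test. That test sets no variance to zero and has no boundary problem.

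Finally, conservatism does not inflate false positives, and at the planned correlation of 0.6 it costs only about 1 point of power. That stands. The planning value was, however, carried over from a retrospective study of renin-angiotensin intervention. Weaker heterogeneity is possible, and there the loss is larger.

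These objections narrow the point without removing it. A likelihood-ratio test run in the customary way would still be miscalibrated, and the plan leaves the choice open.

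**Conclusion.** The point holds as an unstated reference distribution whose customary choice is conservative. With identical fixed effects in both models, chi-square(2) at a nominal 5% has a true size of 3.2% asymptotically and about 2.5% to 3.4% with 20 patients and four periods. The power forgone, measured against the mixture, is about 4 to 7 points at weak to moderate heterogeneity (implied correlations of roughly 0.1 to 0.4) and about 1 point at 0.6. The asymptotic figure follows from theory alone. The simulated ranges rest on assumed variance ratios and normal errors, and the log-scale check also on an assumed correlation, a paired analysis and a different albuminuria measure. The effect is modest and confined to one of several heterogeneity analyses. It is still worth correcting, because a statistic between 3.84 and 5.99 would be significant or not according to a choice that the plan does not make.

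**What to change.** In protocol 10.1 and SAP 5.1:

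1. List treatment and treatment period as fixed effects in both models, fitted by maximum likelihood to the same records, so that they differ only in the slope variance and covariance.
2. State the source of the p-value. With 20 patients, prefer a parametric bootstrap: simulate from the fitted random-intercept model, refit both models to each data set, and report the share of simulated statistics at least as large as the observed one. Fix the number of replicates and the seed in advance.
3. If a closed form is preferred, use half the chi-square(1) tail area plus half the chi-square(2) tail area (5% cut-off 5.14). Note that it stays slightly conservative, at about 3.6% to 3.8%, when the intercept variance is small, as it may be for change scores.
4. State the alpha for this test.

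The preference for the bootstrap rests on that residual conservatism; its own size was not simulated here. The mixture did not exceed 5% in any scenario examined. The cost is a sentence of text and a little computing, with no extra patients or data.

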#### 5.2. Sub group analysis:

The primary and secondary outcomes will be analyzed in the following subgroups by adding a subgroup parameter to the Bayesian hierarchical model as described above:

- 1. Age ( $\geq$  or < 65 years or median)
- 2. Gender (Male / Female)
- 3. Urinary albumin:creatinine ratio (≥ or < 300 mg/g (33.4 mg/mmol) or median)
- 4. eGFR ( $\geq$  or < 60 ml/min/1.73m^2 or median)
- 5. Systolic blood pressure (≥ or < 130 mmHg or median)
- 6. Body mass index ( $\geq$  or  $< 25 \text{ kg/m}^2$  or median)

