#### 2.1. Primary Objective

• To determine the individual response to the SGTL2 inhibitor dapagliflozin in urine albumin-to-creatinine ratio (UACR)

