We will repeat this analysis for the secondary outcomes such as blood pressure, body weight, and several clinical chemistry laboratory parameters, Similar to UACR, we will estimate the posterior probability of a clinically meaningful response and the overall treatment effect. clinically meaningful response as defined as:

• Blood pressure: reduction of 5 mmHg

Statistical Analysis Plan Page 12 of 13

• Body weight: reduction of 3kg

• Hba1c: reduction of 0.5%

• EGFR: reduction of 10% and 3 ml/min.

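### SAP 5.2 splits five continuous factors in 20 patients, at a fixed cut or the median with no rule for which; continuous terms on the treatment effect would keep power and remove the choice

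*Combined protocol and SAP*

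**What the plan says.** SAP 5.2 reads "The primary and secondary outcomes will be analyzed in the following subgroups by adding a subgroup parameter to the Bayesian hierarchical model". Six factors follow. Gender has a single split. Age, UACR, eGFR, systolic pressure and BMI each have a fixed cut with the median as an alternative; for UACR the wording is "300 mg/g (33.4 mg/mmol) or median". Nothing says which cut applies, or when.

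The model referred to is in SAP 5.1. Each patient has an intercept alpha_i and a treatment slope beta_i, with non-informative priors. SAP 5.2 does not say which of the two the subgroup parameter modifies.

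The primary outcome is UACR, and SAP 2.2 names four secondary outcomes. SAP 5.1 words the secondary analysis more loosely: "We will repeat this analysis for the secondary outcomes such as blood pressure, body weight, and several clinical chemistry laboratory parameters". No posterior threshold or other rule for declaring a subgroup effect is given. Protocol section 10 plans no subgroup analysis.

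The only sizing statement, in SAP 3.2 and protocol 4.4, concerns the correlation between the two exposures: "A sample size of 20 patients provides >80% power (alpha 0.05) to detect a correlation coefficient of 0.6".

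**The concern.** The trial asks whether patients truly differ in their response to dapagliflozin. The natural next question is which patients respond, and SAP 5.2 is where the plan would answer it. Three features weaken that answer.

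- Splitting a continuous factor in 20 patients discards much of its information. The protocol's introduction itself describes a graded moderator: UACR lowering tends to be larger at higher baseline UACR.
- An open choice between two cuts gives each continuous factor two chances to show something.
- A subgroup parameter on the intercept describes a difference in level that applies under dapagliflozin and placebo alike. Only a parameter on the treatment slope addresses who responds.

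**Working it through.** **Inputs from the documents.** N = 20 completers (SAP 3.2; protocol 8.5 replaces patients who withdraw after treatment starts). Six factors, five with two cuts, so 5 x 2 + 1 = 11 possible splits (SAP 5.2). Five outcomes at minimum: UACR plus the four in SAP 2.2.

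**Assumptions.** Two-sided 5%, or equivalently a 95% interval excluding zero. With non-informative priors the two behave much alike. The factor and the patient-level response are taken as normal and linearly related with correlation r. The documents do not give the share of patients below each fixed cut, so it is varied.

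**1. The plan's own figure.** By Fisher's z, power = Phi(atanh(r) x sqrt(N - 3) - 1.96). For r = 0.6: atanh(0.6) = 0.693; 0.693 x sqrt(17) = 2.858; 2.858 - 1.96 = 0.898; Phi(0.898) = 81.5%. Simulating the t test for r gives about 84%. The stated figure of more than 80% is reproduced.

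**2. Cost of splitting.** A median split of a normal factor shrinks its correlation with response by sqrt(2/pi) = 0.798. For r = 0.6: 0.6 x 0.798 = 0.479; atanh(0.479) = 0.521; 0.521 x 4.123 - 1.96 = 0.19; Phi(0.19) = 57.5%. Simulation of the t tests at N = 20 gives:

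| True r | Continuous | Median split (10 vs 10) | Fixed cut giving 16 vs 4 |
|---|---|---|---|
| 0.6 | 84% | 60% | 45% |
| 0.5 | 64% | 42% | 31% |
| 0.4 | 43% | 27% | 21% |

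The Fisher approximation gives the same pattern for the median split: 81.5% to 57.5%, 62.0% to 41.4%, and 41.6% to 27.5%.

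**3. Cost of the open cut, UACR only.** One cut per factor gives six comparisons: 1 - 0.95^6 = 26.5%. If either cut may be reported there are 11 overlapping splits. Simulation under no true effect gives about 37% when the fixed cut separates off about 35% of patients, and 38-41% under other assumed shares, including more unequal ones. The independence bound is 1 - 0.95^11 = 43%. The excess shrinks as the fixed cut approaches the median, because the two splits then nearly coincide.

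**4. Across outcomes, one cut each.** 6 factors x 5 outcomes = 30 contrasts. If independent, 1 - 0.95^30 = 78.5%. With correlation of 0 to 0.5 between outcomes and 0 to 0.2 between factors, simulation gives 70-79%.

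**5. After the change.** Continuous terms restore the first column of the table. Six UACR comparisons remain, so the 26.5% of step 3 also remains; the exploratory label deals with that, not the change of method.

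**The case against.** The other side has a fair case. No stated objective depends on SAP 5.2. The analysis is Bayesian and estimates a parameter; no test or threshold is planned, so a 5% error rate is imported. The median reads naturally as a fallback when a fixed cut leaves too few patients on one side, and one sentence stating the trigger would close that gap. Clinical cuts are also familiar to readers. With 20 patients most predictors will be missed whatever the coding: at r = 0.4 even the continuous term has only 43% power.

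Much of this stands. The 5% criterion is an assumption, and sample size is a cause of missed predictors alongside dichotomising. Nothing in the SAP shows an intention to pick cuts after seeing results. But a stated trigger for the median would leave the power loss untouched, and that loss does not depend on how often a false effect would be declared.

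A reader might infer that a spurious predictor of the primary response is likely. The documents do not support that: for UACR alone the chance is 26-41% under the assumed criterion, and it passes one half only when all five outcomes are pooled. A reader might also infer that the four secondary outcomes need to be relabelled as exploratory. They are declared in protocol sections 2 and 8.1.2 and in SAP 2.2, and nothing here calls for changing their status.

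**Conclusion.** The point holds as a cheap improvement to the analysis method. Dichotomising at the median costs about 16 to 24 percentage points of power for true correlations of 0.4 to 0.6, and an unequal fixed cut costs more. This rests on a roughly linear relation and a roughly normal factor. The unspecified choice of cut raises the chance of at least one false subgroup effect on UACR from about 26% to 37-41%, given the assumed 95%-interval criterion and the assumed shares below the fixed cuts. The 70-79% figure applies to the whole table of 30 contrasts and should not be read as a statement about UACR. Separately, the SAP needs to say that the subgroup parameter acts on the treatment effect, since otherwise the analysis may not address response at all.

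**What to change.** In SAP 5.2, replace the cut-points and the median alternative with continuous terms for age, log baseline UACR, eGFR, systolic pressure and BMI. Enter them one at a time, keep gender binary, and let each act on the patient-specific treatment effect beta_i. The log scale for UACR agrees with SAP section 5, which already log-transforms it for regression. Report each term as an estimate with its interval, labelled exploratory. Keep the fixed cuts for descriptive tables only. Leave the status of the four declared secondary outcomes as it is.

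The cost is SAP wording; the data are already to be collected. The downsides are that each term assumes an approximately linear relation on its scale, and that power for weaker predictors remains low with 20 patients.
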